6.6 Follow-up of subjects withdrawn from treatment

The study data of withdrawn patients will be used until the moment of drop-out, unless a patient objects to this.

Patients will be treated according to the best medical judgment of the orthopaedic surgeon, regardless of the study protocol or withdrawal from the study.

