6.1.2 Secondary study parameters/endpoints (if applicable)

Physical functioning, quality of life, pain and patient satisfaction will be scored with PROMs, consisting of: numeric rating scale (NRS) for pain in rest and during loading, Hip disability and Osteoarthritis Outcome Score Physical Short form (HOOS-PS), EQ-5D and an anchor question about general daily functioning. All PROMs will be collected prior to surgery, at 6 months, 1 year, 2 years and 5 years after surgery. All implant related (serious) adverse events including reoperations and survival of the THA (cup and stem component) will be collected up to 5 years after surgery.

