6.4 Withdrawal of individual subjects

Subjects can leave the study at any time for any reason if they wish to do so, without any consequences. They will be asked for the reason for withdrawal, but do not have to answer if they do not want to. Furthermore, the investigator can decide to withdraw a subject from the study for urgent medical or other reasons.

When a patient withdraws from the study, all data collected prior to the moment of withdrawing will be used for study analysis, unless the patient also withdraws consent for use of this data.

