6.4.1 Specific criteria for withdrawal (if applicable)

6.5 Replacement of individual subjects after withdrawal

Subjects for which not enough markers are visible on the first RSA-radiograph will be excluded from the study. These patients will be replaced, to ensure that a minimum of 25 patients per group remain.

Subjects who withdraw from the study for other reasons than the amount of visible markers will not be replaced, as long as a minimum of 20 patients per group remains. Otherwise, additional subjects will be recruited.

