7.4 Follow-up of adverse events

All AEs will be followed until they have abated, or until a stable situation has been reached. Depending on the event, follow up may require additional tests or medical procedures as indicated, and/or referral to the general physician or a medical specialist. SAEs need to be reported till end of study within the Netherlands, as defined in the protocol.

7.5 [Data Safety Monitoring Board (DSMB) / Safety Committee]

The additional risk of the use of the BiMobile cup over and above the risks of standard care, as well as the risk of extra X-rays and the placement of tantalum beads, are deemed to be negligible and therefore no DSMB will be established.

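### The rule that data are used only until withdrawal, including withdrawal by the investigator for medical reasons, is not reconciled with the 5-year reoperation and survival follow-up or with the AE rules

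*Protocol*

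**What the plan says.** Four parts of the protocol bear on a patient who leaves early.

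- **Who may end participation (6.4).** Patients may leave at will. In addition, "the investigator can decide to withdraw a subject from the study for urgent medical or other reasons". The heading for specific withdrawal criteria, 6.4.1, has no text under it in the copy reviewed.
- **What happens to the data (6.4 and 6.6).** Section 6.4 says that, on withdrawal, "all data collected prior to the moment of withdrawing will be used for study analysis", unless consent for that use is also withdrawn. Section 6.6 says: "The study data of withdrawn patients will be used until the moment of drop-out, unless a patient objects to this". The rest of 6.6 concerns care only: "Patients will be treated according to the best medical judgment of the orthopaedic surgeon, regardless of the study protocol or withdrawal from the study".
- **What is to be measured (6.1.2 and 8.2).** "All implant related (serious) adverse events including reoperations and survival of the THA (cup and stem component) will be collected up to 5 years". Section 8.2 analyses implant survival by Cox regression.
- **What the safety section requires (7.4).** "All AEs will be followed until they have abated, or until a stable situation has been reached", and SAEs are to be reported until the end of the study. Neither rule mentions withdrawn patients.

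**The concern.** An implanted cup stays in place whether or not the patient attends study visits, so revision and reoperation remain observable after study procedures stop. Sections 6.4 and 6.6 nevertheless close the data record at withdrawal. They draw no distinction between a patient who withdraws consent and one whom the investigator takes out for a medical reason.

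The second case matters for the survival analysis. Cox regression assumes that, given the model's covariates, a censored patient has the same later risk as those still followed. A patient withdrawn for a medical reason related to the hip may well have a higher risk of revision. Censoring at that point is informative and tends to make the observed revision rate too low. Section 4.3 describes this as the first clinical trial of the BiMobile cup, and with few revisions expected, single events carry the result.

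**Working it through.** The protocol gives no figure for this point, so there is none to reproduce. The check has two parts.

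**1. Following one patient through the text.** Suppose the investigator withdraws a patient at month 8 for a medical reason, the patient does not withdraw consent, and the cup is revised at month 30.

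- *Event that led to withdrawal:* recorded before or at month 8, so it is kept under 6.4 and 6.6.
- *Follow-up of that event:* 7.4 continues until it has resolved or is stable.
- *Revision at month 30:* 6.1.2 would count it, as it falls within 5 years. Section 6.6 would not, as it falls after drop-out. Section 7.4 would have it reported if it qualifies as an SAE, but 7.2.2 does not treat an elective admission as an SAE, so a scheduled revision may not qualify.
- *If it is reported as an SAE:* 7.4 governs follow-up and reporting. Sections 6.4 and 6.6 govern which data are used. The revision could be reported to the ethics committee and still stay out of the Cox analysis.
- *If it is not an SAE:* no procedure would find it. Section 7.2.1 records only relevant AEs that the patient volunteers or staff observe, and a patient without study visits offers fewer occasions for either.

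Under 6.6 as written, this patient contributes 8 event-free months and is then censored.

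**2. Size, for illustration.** Inputs: 25 patients per group (section 3), and the Avantage 5-year revision rate of 4.0% (3.0-5.3) from section 5.4. Assumption: the same rate applies to all three arms. The protocol has no clinical data on the BiMobile cup to support or refute this.

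Expected revisions = n × rate:

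| | 3.0% | 4.0% | 5.3% |
|---|---|---|---|
| Per group (n = 25) | 0.75 | 1.0 | 1.3 |
| All groups (n = 75) | 2.3 | 3.0 | 4.0 |

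The chance of at least one revision in a group of 25 at 4.0% is 1 − 0.96^25 = 0.64 (0.53 at 3.0%, 0.74 at 5.3%).

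Effect of one patient withdrawn early and revised later:

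- One true revision in 25: true 1/25 = 4%, observed 0%.
- Two true revisions in 25: true 2/25 = 8%, observed about 1/24 = 4.2%, since the censored patient leaves the risk set.

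These figures show what a single missed event does. They do not estimate how often it would happen, because the protocol gives no expected rate of investigator withdrawal.

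**The case against.** The strongest reply is section 7.4. It follows every AE until resolved or stable and has SAEs reported to the end of the study, without exempting withdrawn patients. A reader of 6.4 and 6.6 alone might infer that withdrawn patients leave safety follow-up altogether and that their later SAEs go unrecorded. The protocol does not say that, and 7.4 points the other way. What 7.4 does not supply is later implant status or a rule that the later events are analysed.

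Other points on that side:

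- The data sentence in 6.4 speaks of a patient who withdraws, so it can be read as patient-initiated only. Restricting data use is then an ordinary safeguard. This is fair for 6.4, but 6.6 speaks of withdrawn patients in general and makes no exception for investigator withdrawal.
- Complications are not named as a reason for withdrawal. The wording permits this but does not require it, and 6.6 lets a patient be treated on clinical judgement whatever the protocol says, so treating a complication does not force withdrawal. This stands: the frequency is unknown, and nothing in the document shows that it would differ between arms.
- One might infer that 6.4 and 6.6 equate leaving the RSA programme with leaving the study. Neither section mentions RSA. Only the separate baseline marker-visibility rule (3.3, 6.3.1, 6.5) makes that link.
- Section 6.5 says that patients who withdraw for reasons other than marker visibility "will not be replaced, as long as a minimum of 20 patients per group remains". It is tempting to set the 5 of 25 who may be lost without replacement against the 1 expected revision and quote a ratio. That floor covers withdrawals for any other reason, including patients' own choice, so the ratio measures no bias.
- Revision is a secondary outcome that 25 patients per arm cannot estimate precisely: an exact 95% interval is about 0.1-20% for 1/25 and 0-14% for 0/25. This limits the consequence. It does not justify leaving avoidable gaps in so few events.

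**Conclusion.** The point holds as a conflict within the protocol. For a patient withdrawn by the investigator, 6.6 stops data use at drop-out, 6.1.2 requires outcomes to 5 years, and 7.4 keeps AE and SAE duties running; the document does not say which governs. Events up to withdrawal are safe. Later reoperation, revision and survival status have no provision, and followed literally the text gives informative censoring in the Cox analysis.

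The size is small in absolute terms but large relative to the event count: about 1.0 expected revision per arm (0.75-1.3), so one missed revision could take an arm from 4% to 0%. This rests on applying the Avantage rate to every arm and on at least one investigator withdrawal followed by a revision, whose probability the protocol does not allow one to estimate. The point does not concern the primary comparison of two-year RSA migration. A statistical analysis plan could settle which collected data are analysed, but it cannot recover status that was never collected, so the change belongs in the protocol. It is a cheap improvement that should be made.

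**What to change.** In sections 6.4 and 6.6, distinguish three situations: stopping study procedures (RSA, CT or questionnaires), withdrawal by the investigator, and withdrawal of consent by the patient. State that only the last ends data collection. In the other two, implant-related (S)AEs, reoperations and implant survival continue to be collected and are analysed to 5 years, as 6.1.2 plans. Add a sentence to 7.4 saying how its AE and SAE rules apply to withdrawn patients, so that the sections agree.

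The cost is protocol wording and a record check or telephone call for the few patients concerned. No study procedure is added and no rule of clinical care changes.

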6.7 Premature termination of the study

Because the devices used in this study are CE marked and will be used according to its labeling, there are no preconceived reasons for premature termination of the study. Upon the principal investigator's decision to terminate or suspend the study, the involved parties and EC will be notified promptly, stating the reasons.

7. SAFETY REPORTING

7.1 Temporary halt for reasons of subject safety

In accordance to section 10, subsection 4, of the WMO, the sponsor will suspend the study if there is sufficient ground that continuation of the study will jeopardise subject health or safety. The sponsor will notify the accredited EC without undue delay of a temporary halt including the reason for such an action. The study will be suspended

pending a further positive decision by the accredited EC. The investigator will take care that all subjects are kept informed.

7.2 AEs, SAEs and SUSARs

7.2.1 Adverse events (AEs)

Adverse events are defined as any undesirable experience occurring to a subject during the study, whether or not considered related to the RSA procedure or implants. Only relevant adverse events reported spontaneously by the subject or observed by the investigator or his staff will be recorded. The following AE's are directly related to the surgical procedure, and will therefore not be recorded by the investigator: nausea, headache, pain, haemorrhage and wound leakage.

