6.2 Randomisation, blinding and treatment allocation

After signing informed consent, the patients will be randomized in one of the three study groups by the researcher, using an online randomisation program (CASTOR). Patients will be blinded for group allocation. The principal investigator and the participating surgeons may divert from the randomization scheme based on intraoperative findings. Any deviation from the assigned treatment group will be reported as a deviation from protocol.

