8.2 Secondary study parameter(s)

Secondary study parameters concern physical functioning, quality of life, pain, patient satisfaction, device-related complications, reoperations and implant survival. Furthermore, early migration will be compared between the BiMobile 2 mm cement acetabular cup and the Avantage 2 mm cement acetabular cup. The secondary outcomes, will be analysed in the same manner as the primary study parameter, except for implant survival, which will be analysed using Cox regression analysis.

CT data (discharge and 2 years postoperatively) will be analysed using repeated measures ANOVA or mixed models if certain data points are missing.

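### Non-serious events of the operated hip are kept only if judged relevant, and complications count only if judged implant related, apparently by staff who know which cup was placed

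*Protocol*

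**What the plan says.** Protocol section 7.2.1 starts from a wide definition of an adverse event: "any undesirable experience occurring to a subject during the study, whether or not considered related to the RSA procedure or implants". The recording rule that follows is narrower: "Only relevant adverse events reported spontaneously by the subject or observed by the investigator or his staff will be recorded". The word *relevant* is not defined. The section then lists events that "will therefore not be recorded by the investigator: nausea, headache, pain, haemorrhage and wound leakage", without a time limit.

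Section 6.1.2 sets the safety endpoint: "All implant related (serious) adverse events including reoperations and survival of the THA (cup and stem component) will be collected up to 5 years". It gives no criteria for *implant related* and names no assessor. Section 8.2 makes the result an analysed outcome: "Secondary study parameters concern physical functioning, quality of life, pain, patient satisfaction, device-related complications, reoperations and implant survival". Apart from implant survival, these outcomes are to be analysed like the primary parameter.

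On blinding, section 6.2 says "Patients will be blinded for group allocation" and names no other blinded party. In the same section the researcher performs the randomisation, and the principal investigator and surgeons may depart from the allocation because of what they find during surgery. The Study Design section nevertheless calls the trial double blinded.

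**The concern.** Relevance and relatedness would normally be attributes recorded alongside an event. Here they are conditions for the event to enter the data. If the person who applies them knows the cup, the threshold may differ between arms, and the complication counts then mix the performance of the cup with the habits of the assessor.

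The expectations attached to the cups plausibly differ. Section 4.3 says that the BiMobile has no prior clinical studies, and section 5.1 says that the Avantage is the hospital's standard dual mobility cup. Within the BiMobile arms, the surgeon knows whether the standard or the smaller size was used. The bias could go either way: events may be attributed more readily to a new implant, or more readily to the operation.

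This is a rule of data capture. A non-serious event that was never written down cannot be adjudicated later, so no analysis plan can repair the loss.

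**Working it through.** The protocol gives no complication rate and no power for complications, so there is no figure to reproduce. The check is to follow each type of event through the stated rules and then to illustrate the possible size.

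**Step 1: what each rule captures**

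| Type of event | Rule | Does judgement decide entry? |
|---|---|---|
| Serious adverse event, as reported | 7.2.2: all reported, elective admissions excepted | No relevance or relatedness filter |
| Reoperation, survival of cup and stem | 6.1.2: collected by name | Little |
| Serious adverse event, in the complication endpoint | 6.1.2: implant-related events | Yes, through the label |
| Non-serious event of the operated hip | 7.2.1: only if relevant and either volunteered or observed | Yes, and no record remains if rejected |
| Events on the fixed list in 7.2.1 | Never recorded | No; the same list applies to every arm |

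The exposure is therefore rows three and four. Row five loses information, but equally in all arms.

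**Step 2: who judges**

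No section says who decides relevance or relatedness. Section 6.2 leaves patients as the only blinded party, and the power to depart from the allocation during surgery implies that the principal investigator and surgeons know it. The only independent assessment described is the analysis of the RSA images (6.3), which covers migration and not events. Section 7.5 establishes no monitoring board.

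**Step 3: which comparisons are affected**

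Section 8.1 contrasts the 2 mm and 4 mm BiMobile arms, and 8.2 carries that analysis over to the secondary outcomes. For the Avantage contrast, 8.2 names migration only. Section 1 says more generally that BiMobile results will be compared with the Avantage, which may or may not include complications.

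**Step 4: illustration with assumed inputs**

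Let n = 25 per arm (section 2.4), p = true proportion with an event, equal in both arms (assumed 10% to 40%), and r1, r2 = probabilities that an event is recorded or labelled (assumed), with at most one event per patient.

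Expected count in arm i = n × p × ri; false difference = p × (r1 − r2); false ratio = r1 / r2.

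| p | r1, r2 | Expected counts | False difference | Ratio |
|---|---|---|---|---|
| 10% | 0.9, 0.7 | 2.25 v 1.75 | 2 points | 1.29 |
| 20% | 0.9, 0.7 | 4.5 v 3.5 | 4 points | 1.29 |
| 40% | 0.9, 0.7 | 9 v 7 | 8 points | 1.29 |
| 10% | 0.9, 0.5 | 2.25 v 1.25 | 4 points | 1.8 |
| 20% | 0.9, 0.5 | 4.5 v 2.5 | 8 points | 1.8 |
| 40% | 0.9, 0.5 | 9 v 5 | 16 points | 1.8 |

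With r1 = r2 the false difference is 0.

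**Step 5: comparison with chance**

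For p = 20% and r = 0.9, 0.7 the recorded proportions are 0.18 and 0.14. The standard error of their difference is √(0.18 × 0.82/25 + 0.14 × 0.86/25) = √0.01072 = 0.104, or 10.4 points. The false 4 points are 4/10.4 = 0.39 standard errors. In this case the shift is well inside chance variation. It differs from chance in being systematic and invisible in the data.

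**The case against.** The strongest reply is that most of what matters is captured anyway. Section 7.2.2 requires every serious adverse event to be reported, reoperations and survival are named in 6.1.2, loosening is assessed on radiographs (6.1.3), and migration is analysed by an independent party. This stands, and it limits the point to the two gaps in step 1.

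Four stronger readings are tempting, and the documents do not support them.

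- A reader might infer that no adverse event counts unless it is judged relevant or related. Section 7.2.2 contradicts this for the reporting of serious events.
- A reader might infer that 8.2 compares complications between BiMobile and Avantage. It names only migration for that contrast, so a complication comparison rests on the general wording in section 1. In the contrast that 8.2 does carry over, both arms have the same new cup, so a suspicion attached to a new implant cannot separate them; knowledge of the cup size still could.
- A reader might take it as stated that the assessor knows the arm. It is a well-supported inference from 6.2, and the double-blind label in the Study Design section speaks against it.
- A reader might set the illustrated shift beside the 4.0% five-year revision rate in 5.4. That is the wrong benchmark, because reoperations and implant survival are collected by name.

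It is also fair to say that the adverse device event row in Table 2 gives timing and should not be read as a separate recording rule.

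What remains unanswered is that nothing in the protocol defines *relevant* or *implant related*, assigns either judgement to a blinded assessor, or keeps a record of non-serious events that are rejected.

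**Conclusion.** The point holds within these limits. Following sections 7.2.1 and 6.1.2 as written can lose non-serious events of the operated hip for good, and it makes entry into the complication endpoint depend on an undefined label, apparently applied by staff who know the cup. Any comparison of complications between arms can be affected: 2 mm against 4 mm under 8.2, and BiMobile against Avantage if the results meant in section 1 include complications.

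The documents fix neither size nor direction. The illustrated false differences of 2 to 16 percentage points rest entirely on assumed event rates and assumed recording probabilities; they show what is possible and do not estimate a bias. The migration endpoint, the count of reported serious events, reoperations and implant survival are not called into question here. This is a cheap improvement to a stated rule and not a threat to the trial's main result.

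**What to change.** 1. In 7.2.1, 6.1.2 and Table 2, record every adverse event of the operated hip whatever its judged relevance or relatedness, and ask about it with the same question at each contact already scheduled.
2. Reconcile this with the sentence in 7.2.1 that leaves certain events unrecorded without a time limit. As it stands, that sentence would override the new rule for pain, haemorrhage and wound leakage of the operated hip.
3. In 8.2, compare arms on this full count, report relatedness descriptively, and say whether the comparison with the Avantage includes complications.
4. Reconcile the Study Design section with 6.2 on who is blinded, and state who judges relatedness and whether that person knows the cup.

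The cost is protocol wording, some extra data entry for 75 patients, and one short question at existing contacts. These include the 6-week visit, which has no questionnaire in Table 2, and the 5-year contact, which section 10 describes as questionnaires only. No visit is added and no clinical management changes.

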Dual-Mobility (DM) acetabular cups are thought to provide more stability and biomechanically reduce the risk of (early) dislocation compared to regular unipolar acetabular cups.(7-10) Potential disadvantages of DM cups are increased liner wear, psoas impingement and loosening. This might result in more revision surgery at mid- and longer term follow-up for the cemented cups, which has been demonstrated in the Dutch and Australian orthopaedic registries.(11, 12) If the cemented fixation technique improves, this might reduce the number of revisions due to loosening in cemented cups. High quality evidence guiding the best technique for cemented fixation is however lacking. There is evidence that enough bone should be removed, including the removal of the subchondral bone plate; this is known as optimal reaming.(13) The risk of implant loosening might be reduced by increasing the amount of cement used for cup fixation. However, it is currently unknown whether the amount of cement, which depends on the size of the cup, affects stability and survival.(14) To fill this gap in knowledge, this study will compare micro migration of the cup, as an indicator for loosening, in a new dual mobility cup (BiMobile, Waldemar Link GmbH & Co. KG, Hamburg, Germany), using a larger or smaller cup size (and thereby different amounts of cement: approximately 2 millimeter (mm) or 4 mm cement mantle). These results will additionally be compared with the Avantage cup (ZimmerBiomet), which is considered as the standard dual mobility cup in the Netherlands.(15, 16) Migration will be measured with Rontgen Stereophotogrammetry Analysis (RSA), which is currently the gold standard for measuring early migration and predicting long term survival of the implant. A relatively new and less intensive way to measure migration of prostheses is the use of computer tomography (CT) scans, however there is still little scientific evidence on how accurately this can be done.(17-21) This study therefore also measures the accuracy with which migration is measured, between CT scans and RSA.

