4.3 Summary of findings from clinical studies

No clinical studies have been conducted with the BiMobile cup. Current study will be the first clinical trial with this implant.

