10. STRUCTURED RISK ANALYSIS

There is minimal risk associated with participating in this study over and above that of the primary hip arthroplasty procedure. Serious complications may be associated with any total joint replacement surgery. These complications include, but are not limited to: infection; genitourinary disorders; gastrointestinal disorders; vascular disorders, including thrombus; bronchopulmonary disorders, including emboli; myocardial infarction or death.

The devices are CE marked and will be used according to its labelling. Patients will be treated in the best medical judgment of the surgeon, regardless of the study protocol. Assessment involves questionnaires, investigator assessments, RSA-radiographs a CT scan and anterior-posterior and lateral radiographs. The patient's burden from the study consists of two extra CT scans, three extra visits which consist of RSA-radiographs and questionnaires (at 6 months, 1 and 2 years), and at 5 years only questionnaires will be send to the patient. In addition to the benefits from the primary hip arthroplasty procedure e.g.

reduced pain, improved range of motion, patients might benefit from the type of acetabular cup that is used in this study. All study patients receive a dual mobility acetabular cup, instead of a unipolar acetabular cup. Dual mobility cups are assumed to reduce the risk of hip dislocation. Patients may undergo more thorough screening and follow-up than non-study patients and may benefit from this increased surveillance.

The effective radiation dose per RSA-radiograph is 70 μ Sv. Five RSA radiographs, over 5 years of follow-up, will be taken additionally to standard care. Two computed tomography (CT) scans of the hip will be made postoperative. The effective radiation dose per CT of the hip is 0.3 mSv. With this study, a total of 0.95 mSv is taken into account. The annual natural exposure is 2.5 mSv.

11. Attachments

- 11.1 Product Rationale Folder BiMobile
- 11.2 Surgical Technique Folder BiMobile
- 11.3 Brochure Avantage

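### The adverse event list in section 7.2.1 excludes five terms with no time limit and no exception for implant-related events, which conflicts with the 5-year collection rule in section 6.1.2 and Table 2

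*Protocol*

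**What the plan says.** Section 7.2.1 starts broadly: "Adverse events are defined as any undesirable experience occurring to a subject during the study", whether or not the event is thought related to the RSA procedure or the implants. It limits recording to relevant events that the subject reports spontaneously or that the investigator or staff observe. It then takes out five terms. The reason given is "The following AE's are directly related to the surgical procedure", and the consequence is that they "will therefore not be recorded by the investigator: nausea, headache, pain, haemorrhage and wound leakage". No end date, severity limit or causality check is attached.

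Section 6.1.2 sets the collection rule for the secondary endpoint: "All implant related (serious) adverse events including reoperations and survival of the THA (cup and stem component) will be collected up to 5 years". The brackets around the word serious mean that non-serious events are included. Table 2 in section 6.3 likewise has a row for adverse device events, serious or not, with timing at any point in the study.

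Section 8.2 carries this into the analysis: "Secondary study parameters concern physical functioning, quality of life, pain, patient satisfaction, device-related complications, reoperations and implant survival". Pain and device-related complications are separate items in that list.

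**The concern.** The list in section 7.2.1 assigns a cause to an event from its name alone. For nausea or wound leakage in the first days after surgery that is a reasonable way to save effort. Nothing confines it to those days, however, so the same words govern a complaint of pain in year two or year four, including one that the investigator thinks comes from the cup.

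Such complaints bear on an endpoint that the protocol plans to analyse. Staff who apply section 7.2.1 leave them out of the adverse event record. Staff who apply section 6.1.2 put them in. The complication counts would then depend on which section was followed, and an event not logged when it occurred is hard to recover later with its date and attribution. The protocol says of the BiMobile cup that "Current study will be the first clinical trial with this implant", so a complete record of non-serious device events has some value here.

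**Working it through.** No arithmetic underlies this point. The protocol states no adverse event rate, so the check is a comparison of rules applied to example events.

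**Inputs**
- Section 7.2.1: adverse event definition and the five excluded terms.
- Section 7.2.2: all SAEs are reported, no terms are excluded, and an elective admission does not count as serious.
- Section 6.1.2: implant-related events, reoperations and survival to 5 years; NRS pain before surgery and at 6 months, 1, 2 and 5 years.
- Section 6.1.1: RSA at discharge, 6 weeks, 6 months, 1 and 2 years; CT at discharge and 2 years.
- Table 2: device events at any time.
- Section 10: only questionnaires at 5 years.

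**Rules applied to example events**

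| Example event | Section 7.2.1 | Section 6.1.2 and Table 2 | Other capture |
|---|---|---|---|
| Non-serious pain at 18 months, judged implant-related, no diagnosis | Not recorded | Collected | NRS at 1 and 2 years, without onset date or attribution |
| Non-serious haemorrhage or wound leakage, judged implant-related | Not recorded | Collected | None scheduled |
| Loosening or psoas impingement given as a diagnosis | Not on the list, so recordable | Collected | RSA and CT measure migration to 2 years |
| Pain meeting a seriousness criterion | On the list, but section 7.2.2 reports all SAEs | Collected if implant-related | SAE report |
| Pain leading to reoperation | On the list as a symptom | Reoperation collected | Reoperation and survival data |
| Early procedural nausea or wound leakage, not implant-related | Not recorded | Not required | No conflict |

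The first two rows are the conflict: one section says the event is not recorded and another says it is collected. In the remaining rows either the rules agree or another route keeps the event.

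**Where the other routes leave a gap.** NRS scores come at four postoperative points, the first at 6 months, and say nothing of cause. RSA and CT stop at 2 years. Section 6.1.3 would read loosening on standard radiographs, but Table 2 schedules AP and lateral films only before surgery and at discharge, so they cannot be relied on as a late check. From 2 to 5 years, a non-serious problem without a diagnosis or reoperation reaches the record mainly through spontaneous report, and section 7.2.1 removes pain from those reports.

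**Extent.** The rule covers 3 × 25 = 75 patients for up to 5 years, at most 75 × 5 = 375 patient-years. That is exposure to the rule, not a count of lost events.

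**The case against.** The best defence is that section 7.2.1 means only to drop expected procedural events, while implant-related events follow section 6.1.2 and Table 2 in any case. That may well be the intention, but it is not what section 7.2.1 says. Its definition covers events related to the implants, its exclusion is by name, and it makes no exception and no cross-reference. The defence describes the rule that ought to be written.

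Several stronger readings are tempting, and the documents do not support them:

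- *That these events are never recorded or vanish from the safety record.* Section 7.2.2 reports all SAEs and excludes no term, and pain is scored by NRS as an outcome in its own right.
- *That the cup's own failure modes drop out of the endpoint.* The Introduction says "Potential disadvantages of DM cups are increased liner wear, psoas impingement and loosening". None of these is on the excluded list, so each can be recorded as a diagnosis. Pain as a symptom of them is a plausible clinical inference, but the protocol does not state it.
- *That haemorrhage and wound leakage are signals of this cup.* No section ties them to those failure modes. Section 10 treats complications as general to joint replacement: "These complications include, but are not limited to: infection" heads its list.
- *That the rule makes the new cup look as safe as the standard one.* The rule is the same in every arm. If a common share p of events is recorded, the ratio of rates is unchanged, since p·r1 / p·r2 = r1 / r2, while the difference shrinks to p(r1 − r2) and precision falls. A distorted ratio needs p to differ between arms, and nothing in the protocol shows that it would.
- *That the interim safety look is weakened.* Section 8.4 counts SAEs, which an exclusion of non-serious events does not affect.

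These limits narrow the point. They do not remove the conflict over non-serious implant-related events.

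**Conclusion.** The point holds as a conflict between stated rules. Section 7.2.1 forbids recording events that section 6.1.2 and Table 2 require, namely non-serious implant-related events that present under one of the five terms. Late or implant-related pain without a diagnosis is the main case. Followed literally, section 7.2.1 under-ascertains device-related complications in all arms.

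The conclusion rests on two assumptions: that staff apply section 7.2.1 as written, and that some non-serious implant-related events present as an excluded term without a diagnosis. The size of the loss cannot be computed, and neither a direction nor an amount of bias between arms is established. The primary migration endpoint is not touched. This should be corrected, because it affects a planned secondary endpoint and is cheap to put right, but it does not threaten the trial's main conclusion.

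**What to change.** Amend section 7.2.1 so that it and section 6.1.2 give one rule:

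- Limit the exclusion of the five terms to non-serious events within a peri-operative window, whose length the sponsor states.
- State that any such event outside the window, or judged possibly related to the implant at any time, is recorded as an adverse event.
- Cross-refer to section 6.1.2 and to the device-event row of Table 2.

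This changes data recording only, not patient care. It costs a sentence or two in an amendment and a few more adverse event entries. It is best done early, since onset dates and attributions are difficult to reconstruct afterwards.
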